## **5.2.2 Exclusion criteria**

**5.2.2.1** Any serious medical condition, laboratory abnormality, or psychiatric illness that would prevent the subject from signing the informed consent form.

**5.2.2.2** Pregnant or breast feeding females. (Lactating females must agree not to breast feed while taking lenalidomide).

**5.2.2.3** Any condition, including the presence of laboratory abnormalities, which places the subject at unacceptable risk if he/she were to participate in the study or confounds the ability to interpret data from the study.

**5.2.2.4** Renal insufficiency of creatinine clearance < 40 mL/min

**5.2.2.5** Known hypersensitivity to thalidomide or lenalidomide.

**5.2.2.6** The development of erythema nodosum if characterized by a desquamating rash while taking thalidomide or similar drugs.

**5.2.2.7** Concurrent use of other anti-cancer agents or treatments.

**5.2.2.8** Known seropositive for an active viral infection with human immunodeficiency virus (HIV), hepatitis B virus (HBV) or hepatitis C virus (HCV). Patients who are seropositive because of hepatitis B virus vaccine are eligible.

**5.2.2.9** Subjects with hemoglobin < 8.0 g/dL. The use of transfusion with pRBC to correct anemia and meet eligibility criteria will not be allowed.

**5.2.2.10** Patient has an absolute neutrophil count <  $1.0 \times 10^9/L$  within 14 days before enrollment

**5.2.2.11** Peripheral neuropathy of grade 3 or greater. Patients with painful grade 2 neuropathy are also excluded.

**5.2.2.12** Patient has platelet count <  $75 \times 10^9/L$  within 14 days before enrollment.

**5.2.2.13** Plasma cell leukemia at time of study entry.

## **5.3 Visit schedule and assessments**

Screening Assessments and all on study scheduled visits and assessments are outlined in Section 2 Table of Study Assessments.

## 5.4 Drug Administration

### 5.4.1 Treatment assignments

Subjects who qualify for the study will be randomized to either Lenalidomide 15 mg p.o. q.d. days 1-21 of a 28 day cycle or Lenalidomide 25 mg p.o. q.d. for days 1-21 of a 28 day cycle. In addition, dexamethasone (40mg) will be added once a week (Days 1, 8, 15, 22) to the lenalidomide regimen

### 5.4.2 Dosing regimen

The planned dose of lenalidomide for investigation is either 15 or 25 mg/day, orally on days 1 - 21 followed by 7 days rest (28 day cycle). Dosing will be in the morning at approximately the same time each day. **Only enough lenalidomide for one cycle of therapy will be supplied to the patient each cycle.**

Lenalidomide capsules should be swallowed whole, and should not be broken, chewed or opened.

If a dose of lenalidomide is missed, it should be taken as soon as possible on the same day. If it is missed for the entire day, it should not be made up.

Patients who take more than the prescribed dose of lenalidomide should be instructed to contact study staff immediately. Patients should be instructed on secondary contacts, such as a poison control center, should study staff be unavailable.

All subjects will receive dexamethasone 40 mg once a week (Days 1, 8, 15 and 22) with a dose reduction on the same schedule if the patient cannot tolerate the higher dose of dexamethasone (refer to Section 5.5.3).

ASA (81 or 325mg) will be given for anticoagulation prophylaxis. If unable to take ASA then other anticoagulation therapy should be given.

Subjects experiencing adverse events may need study treatment modifications (See section 5.5).

### 5.4.3 Special Handling Instructions

Females of childbearing potential should not handle or administer lenalidomide unless they are wearing gloves.

### 5.4.4 Record of administration

Accurate records will be kept of all study drug administration (including dispensing and dosing) will be made in the source documents.

## 5.5 Dose Continuation, Modification and Interruption

Subjects will be evaluated for AEs at each visit with the NCI CTCAE v3.0 (Appendix D: NCI CTCAE v3.0) used as a guide for the grading of severity.

### 5.5.1 Dose Reduction Steps

Table 1: LENALIDOMIDE Dose Reduction Steps		
Starting Dose	25 mg daily for 21 days every 28 days	15 mg daily for 21 days every 28 days
Dose Level – 1	15 mg daily for 21 days every 28 days	10 mg daily for 21 days every 28 days
Dose Level – 2	10 mg daily for 21 days every 28 days	5 mg daily for 21 days every 28 days
Dose Level – 3	Discontinue treatment	Discontinue treatment

### 5.5.2 Instructions for initiation of a New Cycle

A new course of treatment may begin on the scheduled Day 1 of a new cycle if:

- The ANC is  $\geq 1000/\text{mm}^3$
- The platelet count is  $\geq 50000/\text{mm}^3$
- Any drug-related rash, allergic reaction/hypersensitivity or sinus bradycardia/ other cardiac arrhythmia adverse event that may have occurred has resolved to  $\leq$  grade 1 severity;
- Any other drug-related adverse events that may have occurred have resolved to  $\leq$  grade 2 severity.

If these conditions are not met on Day 1 of a new cycle, the subject will be evaluated weekly and a new cycle of treatment will not be initiated until the toxicity has resolved as described above. If lenalidomide dosing was halted during the previous cycle and was restarted with a one-level dose reduction without requiring an interruption for the remainder of the cycle, then that reduced dose level will be initiated on Day 1 of the new cycle. If lenalidomide dosing was omitted for the remainder of the previous cycle or if the new cycle is delayed due to toxicity newly encountered on the scheduled Day 1, then the new cycle will be started with a one-level dose reduction of lenalidomide. Treatment may be delayed upto 21 days from the original schedule but patients must follow the schedule for subsequent cycles.

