Non-blistering rash Grade 3	
 
If Grade 3, hold (interrupt) lenalidomide dose. Follow weekly.
 
If the toxicity resolves to <math>\leq</math> grade 1 prior to Day 21 of the current cycle, restart lenalidomide at next lower dose level and continue the cycle through Day 21 of the current cycle.
 
	
 
Omit lenalidomide for remainder of cycle.
 
See Instructions for Initiation of a New Cycle and reduce the dose of lenalidomide by 1 dose level at the start of the next cycle. Omitted doses are not made up.
 

Grade 4	
 
Discontinue lenalidomide. Remove patient from study.
 
	
 
Discontinue lenalidomide. Remove patient from study.
 

NCI CTC Toxicity Grade	Onset Day 2-14 of Cycle	Onset ≥ Day 15 of Cycle
Desquamating (blistering) rash- any Grade	
 
Discontinue lenalidomide. Remove patient from study.
 
	
 
Discontinue lenalidomide. Remove patient from study.
 

Neuropathy	
 
If Grade 3, hold (interrupt) lenalidomide dose. Follow at least weekly.
 
If the toxicity resolves to ≤ grade 1 prior to Day 21 of the current cycle, restart lenalidomide at next lower dose level and continue through the scheduled Day 21 of the current cycle.
 
	
 
Otherwise, omit for remainder of cycle and reduce the dose of lenalidomide by 1 dose level at the start of the next cycle. Omitted doses are not made up.
 

Grade 3		
Grade 4	
 
If Grade 4, discontinue lenalidomide. Remove patient from study.
 
	
 
If Grade 4, discontinue lenalidomide. Remove patient from study.
 

Erythema multiforme ≥ Grade 3	
 
Discontinue lenalidomide. Remove patient from study.
 
	
 
Discontinue lenalidomide. Remove patient from study.
 

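### Section 5.5.2 allows a new cycle at a looser neuropathy threshold than Table 2 sets for a mid-cycle restart, and does not define the schedule that follows a delayed cycle

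*Combined protocol and SAP*

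**What the plan says.** **Regimen.** Section 5.4.2 gives lenalidomide "orally on days 1 - 21 followed by 7 days rest (28 day cycle"). Table 1 in section 5.5.1 repeats 21 days in every 28 at each dose level.

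**Delay.** If the conditions for a new cycle are not met on Day 1, section 5.5.2 says that "the subject will be evaluated weekly and a new cycle of treatment will not be initiated until the toxicity has resolved as described above". It ends: "Treatment may be delayed upto 21 days from the original schedule but patients must follow the schedule for subsequent cycles".

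**Recovery before a new cycle.** Section 5.5.2 has two non-hematologic tiers. The stricter one reads "Any drug-related rash, allergic reaction/hypersensitivity or sinus bradycardia/ other cardiac arrhythmia adverse event that may have occurred has resolved to" grade 1 or less. The other reads "Any other drug-related adverse events that may have occurred have resolved to" grade 2 or less. Neuropathy is not named in the stricter tier.

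**Recovery before a mid-cycle restart.** For grade 3 neuropathy with onset on Days 2-14, Table 2 in section 5.5.3 says: "If the toxicity resolves to \leq grade 1 prior to Day 21 of the current cycle, restart lenalidomide at next lower dose level". The later-onset cell omits the rest of the cycle and reduces one level at the next. It gives no recovery grade of its own.

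**The concern.** These rules apply to patients who have just had toxicity, in a multi-center, open-label trial whose purpose is to compare the tolerability of two starting doses.

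On neuropathy, a patient whose grade 3 event has improved to grade 2 by Day 20 may not restart under Table 2. On Day 1 of the next cycle (day 29), still at grade 2, the same patient meets the neuropathy condition of 5.5.2 and may begin a new cycle one dose level lower.

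On timing, the final sentence of 5.5.2 can be followed in several ways that give very different dosing. Two sites could treat identical patients at the same nominal dose level with different numbers of doses and different rest. That would blur comparisons of adverse events, later dose reductions and discontinuations.

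**Working it through.** **1. Recovery thresholds side by side** (Table 2 against section 5.5.2)

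| Toxicity | Mid-cycle restart, Table 2 | New cycle, 5.5.2 | Match |
|---|---|---|---|
| Non-blistering rash, grade 3 | grade 1 or less | grade 1 or less | yes |
| Allergic reaction, grade 2-3 | grade 1 or less | grade 1 or less | yes |
| Bradycardia/arrhythmia, grade 2 | grade 1 or less | grade 1 or less | yes |
| Other non-hematologic, grade 3 or more | grade 2 or less | grade 2 or less | yes |
| Neuropathy, grade 3 | grade 1 or less | grade 2 or less (falls under any other event) | **no** |

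Neuropathy is the only mismatch among these five rows. Platelets also agree: Table 2 equates grade 3 or more with a count below 50,000/mm³, so recovery to grade 2 or less means at least 50,000/mm³, the limit in 5.5.2. The neuropathy row also lacks the pointer to the new-cycle instructions that the rash and thrombocytopenia rows carry.

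**2. Calendar arithmetic**

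Inputs: 21 dosing days and a 28-day cycle (5.4.2), and a delay *d* of 0 to 21 days (5.5.2). Weekly re-evaluation makes 7, 14 and 21 days the natural values. Number days from the original Day 1 of the delayed cycle, so the next original Day 1 is day 29.

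The plan's own figure first: with *d* = 0, rest = 28 − 21 = 7 days, as stated.

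- **Reading A:** original calendar kept, all 21 doses given. Last dose on day 21 + *d*. Rest = 28 − (21 + *d*) = 7 − *d*.
- **Reading B:** original calendar kept, dosing stops at the original Day 21. Doses = 21 − *d*. Rest = 7.
- **Reading C:** later cycles counted from the delayed Day 1. Doses = 21. Rest = 7. Next Day 1 = day 29 + *d*.

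| Delay | A: rest before day 29 | B: doses in delayed cycle | C: next Day 1 |
|---|---|---|---|
| 1 day | 6 days | 20 | day 30 |
| 3 days | 4 days | 18 | day 32 |
| 6 days | 1 day | 15 | day 35 |
| 7 days | 0 days | 14 | day 36 |
| 14 days | none; 7-day overlap with next cycle | 7 | day 43 |
| 21 days | none; 14-day overlap with next cycle | 0 | day 50 |

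Reading A departs from the rest period in 5.4.2, reading B departs from the 21 dosing days, and reading C departs from neither. That is arithmetic, not a view on which rule should be used.

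**The case against.** The strongest reply on timing is that the sentence need not conflict with anything. Read with 5.4.2 and Table 1, the schedule for later cycles may simply be the ordinary 28-day schedule, which is reading C. That is a fair reading. It is not the only one, because the sentence contrasts the delay from the original schedule with a duty to follow the schedule afterwards. Reading B also has support: Table 2 resumes interrupted dosing only through the scheduled Day 21 and does not make up omitted doses. The ambiguity stands; a definite contradiction on timing does not.

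On neuropathy, one can say that the two thresholds govern different decisions and that no patient receives opposite instructions on the same day. That is true, but the protocol uses equal thresholds for the same two decisions in the four comparable rows and gives no reason for the exception. Nothing in the documents suggests that grade 3 neuropathy is common, so few patients may be affected.

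A reader might infer more than the documents support:

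- *That 5.5.2 removes the rest week and imposes 42, 35 or 28 consecutive dosing days after delays of 7, 14 or 21 days.* These runs (days 8-49, 15-49 and 22-49) assume that dosing continues past the original Day 21 and is cut off at day 28. No section states that rule. Total doses over the 49 days would not exceed the planned 21 + 21 = 42, and the next Day 1 still requires the 5.5.2 checks.
- *That the myelosuppression history in section 3.2 shows harm.* That history concerns the 25 mg and 50 mg daily levels beyond Day 28. Under 5.5.2, a cycle delayed for newly encountered toxicity starts one level lower.
- *That the new-cycle threshold should match entry.* Section 5.2.2 says "Patients with painful grade 2 neuropathy are also excluded", which leaves non-painful grade 2 eligible. Entry and continuation limits also differ elsewhere: platelets are 75 × 10⁹/L at entry and 50,000/mm³ for a new cycle.
- *That the arms would be distorted unequally.* The documents give no delay frequency by arm. The 50% and 20% in section 10.5 are assumed dose-reduction rates.

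**Conclusion.** The neuropathy mismatch is definite: grade 1 or less to restart within a cycle, grade 2 or less to begin the next. The timing problem is an undefined term. The rest is lost only if the original calendar is kept **and** dosing runs past the original Day 21, with a delay of at least 7 days. If dosing stops at that day, the loss is in doses instead (14, 7 or 0 remaining). If the calendar restarts, nothing is lost.

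The consequence is possible variation between sites in exposure at the same nominal dose level, falling mainly on safety, later reductions and discontinuations. The effect on the primary outcome (any reduction, section 10.3) should be limited. Under 5.5.2, a cycle delayed for new toxicity, or following one in which dosing was omitted for the remainder, already starts one level lower, so the event is usually counted. This is not universal, since Table 2 allows the dose to be maintained with G-CSF when neutropenia is the only cause. Neuropathy that stays at grade 2 is another route. Under 5.5.2 that patient starts a reduced-dose cycle, which counts as an event; under a grade 1 rule the patient would stay on hold and might never receive a reduced dose.

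The documents give no frequency for delays or for grade 3 neuropathy, so the number of patients affected cannot be stated. No power or sample-size figure depends on this point. It should be corrected, because sites must apply these rules to patients recovering from toxicity.

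**What to change.** Reconcile sections 5.4.2, 5.5.2 and 5.5.3 (Table 2):

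1. Replace the last sentence of 5.5.2 with one that states the date from which later cycles are counted after a delay and how many lenalidomide doses the delayed cycle keeps.
2. Reconcile the neuropathy recovery thresholds in 5.5.2 and Table 2. If a difference between the two decisions is intended, say so, and point the neuropathy row to 5.5.2 as the rash and thrombocytopenia rows do.

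The sponsor's clinicians choose the rules. The statistical need is only that every site applies the same ones. The cost is protocol wording, processed as an amendment under section 8.1, with no added visits or procedures.

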**5.5.3 Instructions for dose modifications or interruption during a cycle.**

Table 2: Dose Modifications		
NCI CTC Toxicity Grade	Onset Day 2-14 of Cycle	Onset <math>\geq</math> Day 15 of Cycle
Grade 3 neutropenia associated with fever (temperature <math>\geq 38.5^\circ\text{C}</math>) or Grade 4 neutropenia	
 
Hold (interrupt) lenalidomide dose.
 
Follow CBC weekly.
 
If neutropenia has resolved to <math>\leq</math> grade 2 prior to Day 21, restart lenalidomide at next lower dose level and continue the cycle through Day 21. If neutropenia is the only toxicity for which a dose reduction is required, G-CSF may be used and the lenalidomide dose maintained
 
	
 
Omit lenalidomide for remainder of cycle
 
See Instructions for Initiation of a New Cycle and reduce the dose of lenalidomide by 1 dose level. Omitted doses are not made up. If neutropenia is the only toxicity for which a dose reduction is required, G-CSF may be used and the lenalidomide dose maintained for the next cycle at the investigators discretion.
 

Thrombocytopenia <math>\geq</math> Grade 3 (platelet count <math>< 50,000/\text{mm}^3</math>)	
 
Hold (interrupt) lenalidomide dose.
 
Follow CBC weekly.
 
If thrombocytopenia resolves to <math>\leq</math> grade 2 prior to Day 21, restart lenalidomide at next lower dose level and continue the cycle through Day 21 of the current cycle.
 
Hold prophylactic anti-coagulation, if applicable.
 
Restart prophylactic anti-coagulation when platelet count is <math>\geq 50,000/\text{mm}^3</math>.
 
	
 
Omit lenalidomide for remainder of cycle
 
See Instructions for Initiation of a New Cycle and reduce the dose of lenalidomide by 1 dose level at the start of the next cycle. Omitted doses are not made up.
 
Hold prophylactic anti-coagulation, if applicable.
 
Restart prophylactic anti-coagulation when platelet count is <math>\geq 50,000/\text{mm}^3</math>.
 

Non-blistering rash Grade 3	
 
If Grade 3, hold (interrupt) lenalidomide dose. Follow weekly.
 
If the toxicity resolves to <math>\leq</math> grade 1 prior to Day 21 of the current cycle, restart lenalidomide at next lower dose level and continue the cycle through Day 21 of the current cycle.
 
	
 
Omit lenalidomide for remainder of cycle.
 
See Instructions for Initiation of a New Cycle and reduce the dose of lenalidomide by 1 dose level at the start of the next cycle. Omitted doses are not made up.
 

Grade 4	
 
Discontinue lenalidomide. Remove patient from study.
 
	
 
Discontinue lenalidomide. Remove patient from study.
 

NCI CTC Toxicity Grade	Onset Day 2-14 of Cycle	Onset ≥ Day 15 of Cycle
Desquamating (blistering) rash- any Grade	
 
Discontinue lenalidomide. Remove patient from study.
 
	
 
Discontinue lenalidomide. Remove patient from study.
 

Neuropathy	
 
If Grade 3, hold (interrupt) lenalidomide dose. Follow at least weekly.
 
If the toxicity resolves to ≤ grade 1 prior to Day 21 of the current cycle, restart lenalidomide at next lower dose level and continue through the scheduled Day 21 of the current cycle.
 
	
 
Otherwise, omit for remainder of cycle and reduce the dose of lenalidomide by 1 dose level at the start of the next cycle. Omitted doses are not made up.
 

Grade 3		
Grade 4	
 
If Grade 4, discontinue lenalidomide. Remove patient from study.
 
	
 
If Grade 4, discontinue lenalidomide. Remove patient from study.
 

Erythema multiforme ≥ Grade 3	
 
Discontinue lenalidomide. Remove patient from study.
 
	
 
Discontinue lenalidomide. Remove patient from study.
 

Sinus bradycardia/ other cardiac arrhythmia	
 
Hold (interrupt) lenalidomide dose. Follow at least weekly.
 
If the toxicity resolves to ≤ grade 1 prior to Day 21, restart lenalidomide at next lower dose level and continue the cycle through Day 21.
 
	
 
Omit lenalidomide for the remainder of the cycle.
 
See Instructions for Initiation of a New Cycle and reduce the dose of lenalidomide by 1 dose level.
 

Grade 2		
≥ Grade 3	
 
Discontinue lenalidomide. Remove patient from study.
 
	
 
Discontinue lenalidomide. Remove patient from study.
 

NCI CTC Toxicity Grade	Onset Day 2-14 of Cycle	Onset ≥ Day 15 of Cycle

Allergic reaction or hypersensitivity
 
Grade 2-3
 
Grade 4
	
 
Hold (interrupt) lenalidomide dose. Follow at least weekly.
 
If the toxicity resolves to ≤ grade 1 prior to Day 21, restart lenalidomide at next lower dose level and continue the cycle through Day 21.
 
Discontinue lenalidomide. Remove patient from study.
 
	
 
Omit lenalidomide for the remainder of the cycle.
 
See Instructions for Initiation of a New Cycle and reduce the dose of lenalidomide by 1 dose level.
 
Discontinue lenalidomide. Remove patient from study.
 

Venous thrombosis/embolism ≥ Grade 3
	
 
Hold (interrupt) lenalidomide and start anticoagulation; restart lenalidomide at investigator's discretion (maintain dose level). See Anticoagulation Consideration (Section 5.6.1.2)
 
	
 
Omit lenalidomide for remainder of cycle. See Anticoagulation Consideration (Section 5.6.1.2)
 


other non-hematologic toxicity ≥ Grade 3
	
 
Hold (interrupt) lenalidomide dose. Follow at least weekly.
 
If the toxicity resolves to ≤ grade 2 prior to Day 21 restart lenalidomide and continue through the scheduled Day 21 of the current cycle.
 
	
 
Omit lenalidomide for remainder of cycle. Omitted doses are not made up.
 
See Instructions for Initiation of a New Cycle and reduce the dose of lenalidomide by 1 dose level when restarting Lenalidomide at the start of next cycle.
 

Hyperthyroidism or hypothyroidism
	
 
Omit lenalidomide for remainder of cycle, evaluate etiology, and initiate appropriate therapy.
 
See Instructions for Initiation of a New Cycle and reduce the dose of lenalidomide by 1 dose level.
 
	
 
Omit lenalidomide for remainder of cycle, evaluate etiology, and initiate appropriate therapy.
 
See Instructions for Initiation of a New Cycle and reduce the dose of lenalidomide by 1 dose level.
 

Dexamethasone (40 mg) will be administered at a dose of 40mg once a week (Days 1, 8, 15 and 22) to the Lenalidomide regimen, with a dose reduction to 20mg on the same schedule if the patient cannot tolerate the higher dose of dexamethasone.

Grade 3 or 4 toxicity attributable to dexamethasone (e.g., proximal myopathy, glucose intolerance uncontrolled by insulin) may warrant dose modification of dexamethasone to 20 mg on the same schedule. If patient continues to have dexamethasone related toxicity then dexamethasone will be discontinued and lenalidomide will be continued as single agent as long as the response criteria are satisfied.

#### **5.5.4 Treatment compliance**

At all times, when dispensing study drug, research center personnel will review the dosing instructions, printed on the packaging, with subjects. Subjects will be asked to maintain a diary to record the drug administration. Subjects will be asked to bring any unused study drug to the research center at their next visit. Research personnel will count and record the number of used and unused study drug capsules at each visit and reconcile with the patient diary.

### **5.6 Concomitant therapy**

#### **5.6.1 Recommended concomitant therapy**

Subjects should receive full supportive care, including transfusions of blood and blood products, antibiotics, and antiemetics when appropriate.

##### **5.6.1.2 Anticoagulation Consideration**

Lenalidomide increases the risk of thrombotic events in patients who are at high risk or with a history a thrombosis, in particular when combined with other drugs known to cause thrombosis. When lenalidomide is combined with other agents such as steroids (e.g. dexamethasone, prednisone), anthracyclines (Doxil, Adriamycin) and erythropoietin the risk of thrombosis is increased.

Daily aspirin (81 or 325 mg) or some other form of prophylaxis as deemed appropriate is required. Low molecular weight heparin may be utilized in patients that are intolerant to ASA. Coumadin should be used with caution and close monitoring of INR.

